6. SELECTION OF SUBJECTS

The inclusion of 120 patients who have been diagnosed with cancer in stages I-III and who are going to start chemotherapy treatment is proposed. Once the treatment is finished, the degree of cutaneous comfort will be compared between the patients who have developed peripheral neuropathy in both groups.

6.1. Inclusion criteria

Patients must meet all the criteria that appear in this section to be included in the study.

- To be older than 18 years old.
- To be able to complete questionnaires.
- Give informed consent in writing.
- Being able to apply the product under test by oneself.
- To have been diagnosed with stage I-III primary cancer.
- To have received a maximum of one treatment session with chemotherapy (derivatives of taxane, platinum or vincristines).
- Eastern Cooperative Oncology Group (ECOG) performance status (PS) 0-2.
- Life expectancy greater than or equal to 6 months.

6.2. Exclusion criteria

Patients who meet one or more of the following criteria will not be eligible to take part in the study despite meeting all the requirements of section 6.1:

- Not being or having been treated with antidepressants, antiepileptics or HIV medication in the last 3 months.
- Pre-existing peripheral neuropathies not related to chemotherapy treatment.
- Pre-existing neurodegenerative or neuromuscular disease or history of stroke.
- Family history of neuropathic diseases.
- Having suffered in the last 6 months: myocardial infarction, unstable angina, stroke, transient ischemic attack, decompensated heart failure requiring hospitalization or class III/IV heart failure.
- Being receiving investigational treatment (being involved in a clinical trial).
- Evidence or indication of metastasis affecting the Central Nervous System.
- Use of immunosuppressive or immunomodulatory medication that may lead to immunodeficiencies.
- Not being treated with topical palmar and/or plantar medication.
- Known hypersensitivity to capsaicin.
- Having reduced capacity for expression or response to forms.
- Not have been under general anesthesia for at least one month before starting the study.
- Complication of peripheral polyneuropathy symptoms that require the use of specific medication.

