3. INTRODUCCIÓN

The impact of cancer in the western world and the growing number of people affected each year¹ means that new, increasingly effective and selective treatments are appearing relatively quickly. However, although these treatments are highly effective in killing tumour cells, they are not their only target. Molecules used in cancer treatments often affect healthy cells, causing side effects (nausea, diarrhoea, anaemia, immunosuppression, fatigue and hair loss). When antineoplastic therapies affect the sensory peripheral nervous system, they can cause peripheral polyneuropathy (NP or CIPN (Chemotherapy-Induced Peripheral Neuropathy)). The prevalence of this disease varies depending on the chemotherapy agent administered, affecting up to 80% of patients treated with taxanes (paclitaxel and/or docetaxel) or up to 95% of patients treated with oxyplatin². People with PN experience sensory discomfort, mainly in the extremities (numbness, dryness, tingling, burning, stinging, allodynia or hyperalgesia)³ which, over time, can

lead to the interruption of cancer treatment, with the risks that this entails. This condition often persists after the end of cancer treatment, which greatly affects the quality of life of those who suffer from it, as it can be uncomfortable when working, playing sports, carrying out household chores and even when socialising. In addition, the uncomfortable sensations can disturb sleep, which has an impact on mood. In general, people with NP caused by cancer treatments feel a great dissatisfaction with their skin.

Currently, there is no effective treatment for NP, and when the symptomatology is severe and limits patients' daily life, some doctors recommend taking antidepressants, such as duloxetine, or discontinuing chemotherapy treatment⁴. Although a number of clinical trials aimed at finding an effective treatment for NP have been conducted in recent years, none of them have proven to be effective. Therefore, understanding the mechanisms governing the development of PN and its treatment is a huge challenge in oncology as it is one of the main causes of chemotherapy withdrawal.

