7. PRODUCT DESCRIPTION

7.1. Product

Subjects who meet the inclusion/exclusion criteria and who become part of the study may take any medication that their physician deems appropriate, excluding those specified in the exclusion criteria.

Patients participating in the study will apply:

Cosmetic creams Ref. PB-011 and PB-012.

Tradename: Nocisens.

Business owner: Prospera Biotech S.L.

Composition:

- PB-011: Capric Triglyceride, Glyceryl Behenate, Glyceryl Stearate, Hydrogenated Castor Oil, Diethylene Glycol Monoethyl Ether, Tocopherol, Hydroxymethoxyiodobenzyl Glycolamide Perlargonate.
- PB-012: Capric Triglyceride, Glyceryl Behenate, Glyceryl Stearate, Hydrogenated Castor Oil, Diethylene Glycol Monoethyl Ether, Tocopherol.

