7.2. Study development

When a subject meets all the inclusion criteria and none of the exclusion criteria and has signed the informed consent document, he/she is electable to enter the study. The researchers will collect the data of each volunteer and notify Prospera Biotech of their inclusion. Patients will

receive the cream when they start the chemotherapy treatment. Creams will be either sent directly to the participants' home or sent in advance to the centers and stored there at room temperature (15-25°C) until distributed to participants. The principal investigator will create the Data Notebook for each subject, anonymizing the personal and clinical data in all cases. The type of product to be assigned will be determined by the randomization procedure.

Subjects taking part in the study should apply a sufficient amount of cream to their hands once a day for the duration of their chemotherapy treatment. Those subjects who develop skin sensitivity or peripheral neuropathy should undergo the following procedures:

1. Increase the frequency of use of the cream to twice a day in all affected areas.
2. Once the chemotherapy treatment is finished: evaluation of the degree of skin satisfaction by means of a questionnaire that assesses the Dermatology Life Quality Index [DLQI] (Annex II) and the degree of satisfaction with the cream (Annex IV). Evaluation of the discomfort generated by peripheral neuropathy through a follow-up questionnaire (Annex III). Measurement of skin sensitivity using Von Frey hairs for patients who voluntarily wish to do so. These procedures will be carried out by the study collaborators of each center. In case of need, Prospera Biotech team could also contribute to make the follow-up (questionnaires) telematically.

The study procedures are included in section 8.2.

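### Three of the 13 exclusion criteria in section 6.2 are worded with reversed polarity, so read literally they bar unexposed patients; the two medication items also sit against section 7.1

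*Combined protocol and SAP*

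**What the plan says.** The rule that governs the exclusion list opens section 6.2: "Patients who meet one or more of the following criteria will not be eligible to take part in the study". Section 7.2 applies the same rule at entry: "When a subject meets all the inclusion criteria and none of the exclusion criteria and has signed the informed consent document".

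Three of the 13 items under that rule begin with a negation:

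- "Not being or having been treated with antidepressants, antiepileptics or HIV medication in the last 3 months"
- "Not being treated with topical palmar and/or plantar medication"
- "Not have been under general anesthesia for at least one month before starting the study"

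The other ten name the disqualifying condition directly. One of these is itself a medication item: "Use of immunosuppressive or immunomodulatory medication that may lead to immunodeficiencies".

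On concomitant treatment, section 7.1 says that enrolled subjects "may take any medication that their physician deems appropriate, excluding those specified in the exclusion criteria". The introduction (section 3) notes that when neuropathy symptoms are severe, "some doctors recommend taking antidepressants, such as duloxetine".

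**The concern.** Under a heading where meeting an item disqualifies, an item that says a patient has not had an exposure disqualifies the unexposed. Three items do this, and the ten around them do not, so no list-wide convention lets the reader reverse all of them safely. Eligibility is an operative rule that each centre of a multicentre study has to apply, so this is a wrong instruction and not a missing detail.

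Two things are at stake. First, patients who fit what the sponsor apparently meant are, on the text, enrolled in breach of an exclusion criterion. Section 7.3 lets the investigator withdraw subjects for such a breach, and section 11.2 requires each eligibility deviation to be documented and telephoned to the monitor. Second, centres that resolve the wording differently would enrol different kinds of patient. Some could be taking antidepressants, which section 3 says are used for the condition under study. That would add variation to the skin-comfort outcome.

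**Working it through.** **Literal against apparent reading.** Let A be current use, or use in the last 3 months, of the systemic medicines in the first item; B current topical treatment of the palms or soles; and C general anaesthesia within the month before the study.

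| Item | Literal text excludes | Apparent intent excludes |
|---|---|---|
| Systemic medicines | patients without A | patients with A |
| Topical treatment | patients without B | patients with B |
| Anaesthesia | patients without C | patients with C |

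Because one item is enough to exclude:

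- eligible on the literal text: A and B and C all present;
- eligible on the apparent intent: A, B and C all absent.

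No patient can be in both groups, so they are disjoint. They are not complements: a patient with one or two of the exposures is excluded under either reading.

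**A second parse of the first item.** It could be read as (not being treated) or (having been treated). That would exclude almost everyone, so it does not rescue the wording.

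**Check against the rest of the protocol.** Sections 6, 6.1 and 6.3 describe adults with stage I–III cancer who are about to start chemotherapy or have had at most one session. None of them requires A, B or C.

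**Check against section 7.1.** That section treats the medicines named in the exclusion list as not allowed on study.

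- Topical item: the literal text requires current use and 7.1 bars it. This is a direct conflict.
- Systemic item: a patient currently on these medicines passes the literal text but breaches 7.1. One who stopped within the last 3 months satisfies both. The conflict is partial.
- Anaesthesia item: 7.1 concerns medication and does not address it.

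**How few would pass literally.** The documents give no exposure rates. The figures below are assumptions, with the three exposures taken as independent. Literal pass rate = a × b × c; reversed pass rate = (1 − a)(1 − b)(1 − c).

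| a (systemic) | b (topical) | c (anaesthesia) | Literal | Reversed |
|---|---|---|---|---|
| 5% | 2% | 5% | 0.05 × 0.02 × 0.05 = 0.005% | 0.95 × 0.98 × 0.95 = 88.4% |
| 15% | 5% | 20% | 0.15 × 0.05 × 0.20 = 0.15% | 0.85 × 0.95 × 0.80 = 64.6% |
| 30% | 10% | 40% | 0.30 × 0.10 × 0.40 = 1.2% | 0.70 × 0.90 × 0.60 = 37.8% |

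Even at the most generous row, enrolling 120 on the literal text would mean screening 120 / 0.012 = 10,000 otherwise eligible patients, against 120 / 0.378 ≈ 318 with the items reversed.

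**The plan's sample size is not affected.** With the section 6.3 inputs (difference 2, SD 3, 95% power) and a two-sided 5% test assumed, n per arm = 2 × (1.960 + 1.645)² × 3² / 2² ≈ 58.5, rounded up to 59. The t-based calculation gives 59.5, rounded up to 60, with 95.2% power. The stated 60 per arm reproduces and does not depend on these three items.

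**The case against.** The strongest reply is that the intent is recoverable. Section 7.1 signals the direction for the medicines, no section describes a population that must be exposed, and the literal reading would leave so few patients that any centre applying it would notice at once. The text also carries leftover Spanish in places, so a translation slip is plausible, though it cannot be verified. Nothing in the documents shows that any centre misread the items. All of this limits the practical harm. It does not remove the defect: a centre that follows the presumed intent enrols patients against the written protocol.

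Several stronger readings are tempting, and the documents do not support them:

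- A reader might infer that all three items contradict section 7.1. As worked through above, only the topical item does so squarely, the systemic item does so in part, and the anaesthesia item not at all.
- A reader might infer that mixed enrolment confounds the comparison of the creams. A centre's reading of eligibility applies to both randomised arms, so the expected effect is added variation and a less clearly defined population. Section 3 also names only antidepressants as used for neuropathy, not the other classes in the first item.
- A reader might infer that affected patients fall out of the per-protocol set. Section 12 defines that set by how subjects conduct themselves on study and does not mention eligibility.
- A reader might infer that the two readings give mirror-image populations. They are disjoint, but many patients are excluded under both.

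**Conclusion.** The point holds: three of the 13 exclusion items give the wrong result as written, and this should be corrected. That conclusion rests on the text alone. The eligible populations under the literal and apparently intended readings have no patient in common. The 0.005% to 1.2% literal pass rate is only an illustration, resting on assumed prevalences and independence, and no conclusion depends on a particular value in that range.

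The consequences are that patients who fit the apparent intent count as eligibility deviations on the text, and that centres reading it differently could enrol a mixed population with more variable outcomes. On this point, the validity of the between-arm comparison is protected by randomisation. Which direction each item should take is for the sponsor to confirm; this review does not decide it.

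**What to change.** The sponsor should:

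1. confirm the intended direction of each of the three items;
2. reconcile sections 6.2 and 7.1 on the medicines concerned;
3. restate each item so that its polarity matches the heading it sits under;
4. send the corrected list to all centres.

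If any medication item is moved to the inclusion criteria in section 6.1, section 7.1 must be amended at the same time. Its restriction refers only to medicines named among the exclusion criteria, so an item moved without that edit would drop out of the restriction.

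The cost is one short protocol amendment, which under section 11.4 needs Ethics Committee approval. The sample size does not change.

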2.3. Description of the products under study

Product: Cosmetic creams with Ref. PB-011 and PB-012

Trade name: Nocisens. The formulation with the best acceptance in the study population will be marketed under the name Oncapsisens.

Commercial name: Prospera Biotech S.L

Code and INCI:

- PB-011: Capric Triglyceride, Glyceryl Behenate, Glyceryl Stearate, Hydrogenated Castor Oil, Diethylene Glycol Monoethyl Ether, Tocopherol, Hydroxymethoxyiodobenzyl Glycolamide Perlargonate.
- PB-012: Capric Triglyceride, Glyceryl Behenate, Glyceryl Stearate, Hydrogenated Castor Oil, Diethylene Glycol Monoethyl Ether, Tocopherol.

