6.3. Expected number of subjects and justification

A total of 120 volunteers diagnosed with any type of cancer, in stages I-III, who are about to start or have received a maximum of 1 dose of chemotherapy treatment will be studied.

Two study populations are contemplated: (i) population that will receive the PB-011 cream; (ii) population that will receive the PB-012 cream. Both populations will apply the cream on their hands once a day. If sensory discomfort or, in the worst case, peripheral neuropathy appear during the chemotherapy treatment period, the application will be increased to twice daily on the affected areas (generally hands and feet).

The number of volunteers for the study is 60 for each population. This value is based on: (i) a difference of 2 points between both populations (PB-011 and PB-012), on a satisfaction scale of

0 to 10 points, with 0 being very dissatisfied and 10 very satisfied, or 2 points on the Von Frey scale; (ii) a variability (standard deviation) of 3 points in each population; (iii) a p-value of statistical significance <0.05 and, (iv) a probability of finding a statistically significant difference for the p-value <0.05 of 95%.

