9. ADVERSE EVENTS

An adverse event is considered to be any adverse medical event that occurs in a clinical research subject to whom a product has been administered, even if it does not necessarily have a causal relationship with this treatment. An adverse event can also be any unfavorable or unexpected sign, including an abnormal laboratory finding, symptom, or illness temporarily associated with the use of an investigational product, related or not. An adverse event is considered to be any adverse medical event that occurs in a clinical research subject to whom a product has been administered, even if it does not necessarily have a causal relationship with its use. An adverse event can also be any unfavorable or unexpected sign, including an abnormal laboratory finding, symptom, or illness temporarily associated with the use of an investigational product, related or not.

Due to the fact the products in study are already commercialized, no adverse effects are expected. However, the recording of adverse events is an important aspect of study documentation, so the rules to follow are described below:

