ANNEX IV: SATISFACTION QUESTIONNAIRE

Title: Study for the evaluation of the degree of skin satisfaction of cosmetic creams PB-011 and PB-012 for sensitive skin in oncological patients affected by a palmoplantar polyneuropathy secondary to taxanes.

Principal Investigator: [name]

Reference: 20PB-02

1. Has applying the cream to your hands and/or feet caused you any discomfort?

Nothin									Many
1	2	3	4	5	6	7	8	9	10

2. Has the application of the cream to your hands and/or feet generated any kind of skin reaction?

Nothin									Many
1	2	3	4	5	6	7	8	9	10

3. How would you define your degree of satisfaction with the cream?

Nada									Mucho
1	2	3	4	5	6	7	8	9	10

If, sensorial discomfort or CIPN have appeared during the chemotherapy treatment please answer also:

1. When you apply the cream to your hands and/or feet, do you feel any relief from any of the sensations that bother you?

YES	NO
-----	----

2. Has the application of the cream generated comfort in your skin sensitivity on the hands

and/or feet?

Nothing										A lot
1	2	3	4	5	6	7	8	9	10	

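### The only hypersensitivity exclusion is to capsaicin, which neither cream lists; known allergy to the six shared ingredients is not screened for

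*Combined protocol and SAP*

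**What the plan says.** Among the exclusions in section 6.2, the one that deals with allergy reads "Known hypersensitivity to capsaicin".

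Section 7.1 gives the composition of the two creams, and section 2.3 gives the same lists. The shorter list is "PB-012: Capric Triglyceride, Glyceryl Behenate, Glyceryl Stearate, Hydrogenated Castor Oil, Diethylene Glycol Monoethyl Ether, Tocopherol". The list for the other cream, PB-011, repeats these six ingredients and ends with one more (quoted in the working below).

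Section 7.2 sets the entry rule: "When a subject meets all the inclusion criteria and none of the exclusion criteria and has signed the informed consent document", the patient can join the study. On exposure, section 6.3 states: "Both populations will apply the cream on their hands once a day". Application lasts as long as chemotherapy (2.7, 7.2) and goes to twice daily on affected areas if discomfort or neuropathy appears.

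On harm, section 9 says: "Due to the fact the products in study are already commercialized, no adverse effects are expected". It then adds that adverse events must still be recorded, and sets out how.

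**The concern.** A hypersensitivity exclusion for a topical product would normally be tied to what the product contains. Here the named substance is in neither list, and the substances that are listed have no criterion naming them. The written rule therefore admits a patient who already knows that they react to one of the shared ingredients. That patient would apply the cream every day during chemotherapy.

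What is at stake is an avoidable skin reaction in a patient undergoing cancer treatment. A secondary question is whether such reactions could disturb the satisfaction results, since Annex IV asks: "Has the application of the cream to your hands and/or feet generated any kind of skin reaction".

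**Working it through.** The main check compares texts; the plan states no figure to reproduce.

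**1. Eligibility criteria.** Section 6.1 has 8 inclusion criteria, and none mentions allergy or hypersensitivity. Section 6.2 has 13 exclusion criteria, of which 1 concerns hypersensitivity (capsaicin).

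**2. Composition (2.3 and 7.1).** PB-012 has 6 listed ingredients. PB-011 has the same 6 plus 1 more, which closes its list: "Tocopherol, Hydroxymethoxyiodobenzyl Glycolamide Perlargonate". That makes 6 + 1 = 7 distinct ingredients. Capsaicin is named in 0 of the 2 lists, and the word occurs nowhere else in the text supplied.

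**3. Criteria against composition.**

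| Substance | In PB-011 | In PB-012 | Hypersensitivity criterion in 6.2 |
|---|---|---|---|
| Capsaicin | not listed | not listed | yes |
| Six shared ingredients | yes | yes | none |
| Additional PB-011 ingredient | yes | no | not named; possibly meant through capsaicin, but not stated |

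**4. Consequence under the entry rule.** Section 7.2 requires every inclusion criterion, no exclusion criterion, and consent. Known allergy to a shared ingredient fails none of these, so the patient is eligible in either arm.

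**5. Other safeguards.** Section 7.3 lets the subject withdraw at any time, and lets the investigator withdraw a subject after a serious or unexpected adverse event. Section 9.1 requires events to be recorded and followed up. Section 10.2 requires risks to be explained before consent. The first two act after exposure. The third informs the patient but does not make allergy a reason not to enrol.

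**6. Possible effect on the comparison (illustration only).** Suppose k patients in one arm of n each score d points lower because of a reaction, and none do in the other arm. The arm mean then shifts by k × d / n. The values k = 2 and d = 5 are assumptions; n = 60 is from section 6.3.

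- Whole arm: 2 × 5 / 60 = 0.17 points.
- If only half the arm completes the end-of-treatment questionnaires (assumed n = 30) and both cases are among them: 2 × 5 / 30 = 0.33 points.

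Section 6.3 plans for a difference of 2 points with a standard deviation of 3 on a 0 to 10 satisfaction scale. Even these one-sided cases amount to 0.17 / 2 = 8% and 0.33 / 2 = 17% of the planned difference.

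**The case against.** **Capsaicin may be a proxy.** The criterion may be aimed at the additional PB-011 ingredient, and the planned trade name in section 2.3, Oncapsisens, could be read as a hint of that. A reader might infer from the lists that none of the seven ingredients is covered. The documents do not support so firm a count, because matching names cannot settle what the criterion was meant to catch. This part of the objection stands. It leaves the six shared ingredients, and so the whole of PB-012, without a criterion.

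**The result is not materially threatened.** A reader might infer that allergic reactions would bias the comparison. Both creams contain the six shared ingredients, so randomisation spreads such reactions over the arms by chance, which adds noise and no systematic bias. A reaction to the PB-011-only ingredient is part of the difference between the products, which the trial sets out to measure (section 4). This stands, and it is why the point rests on patient safety alone.

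**Unseen material may help.** Section 10.4 refers to product instructions, which are not supplied. Annex I (the Data Notebook) is only referenced, and consent pages were removed before review. An allergy warning or a history field could be in any of these, and investigators may screen out such patients in practice. This lowers the chance that the gap causes harm. It does not create an exclusion criterion, and section 7.2 decides entry on the criteria.

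**The products are described as marketed.** Section 9 relies on this to expect no adverse effects. That may bear on risk for users in general, but it gives no protection to someone with a known allergy to an ingredient.

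**Conclusion.** The point holds as a minor patient-safety gap in the eligibility rule. Section 6.2 and the composition in 7.1 do not match. No criterion covers known hypersensitivity to the six ingredients common to both creams, and coverage of the seventh is unstated. A patient with a known allergy to a shared ingredient meets the entry rule and would apply the cream daily throughout chemotherapy.

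The conclusion rests on the criteria and ingredient lists as printed, which show no visible gaps. It assumes that no unseen document adds an eligibility criterion.

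Two further claims would go too far. The number of patients affected cannot be given, because the documents contain no allergy frequency. Nor do they show that the comparison between arms would be distorted: the shifts of 0.17 to 0.33 points come from assumed inputs and serve only to show that the effect is likely small.

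**What to change.** Reconcile the hypersensitivity criterion in section 6.2 with the composition in section 7.1:

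- Keep the capsaicin criterion and state why it is there, including whether it is meant to cover the additional PB-011 ingredient.
- Extend it to known hypersensitivity to any listed ingredient of PB-011 or PB-012. Applied before allocation and to both creams alike, this leaves the comparability of the arms untouched.
- Check it with one question at screening and record the answer in the Data Notebook.

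The cost is a one-line amendment, with the ethics committee review that section 11.4 requires, and one added question. Possibly a few patients become ineligible. The sample size calculation and the analysis do not change.

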7.3. Withdrawal criteria

Based on the provisions of the Declaration of Helsinki, the subjects have the right to withdraw from the study at any time and for any reason, being able to express it personally or through their representative. The investigator reserves the right to withdraw any subject from the study in the following cases:

- Subject abandonment: violation of inclusion or exclusion criteria or non-cooperation. In case of withdrawal, the reason is reflected in the Data Notebook.
- By efficacy criteria: if, in the investigator's opinion, the product is not causing any benefit to the subject under study.
- Due to safety criteria: in the event of a serious or unexpected adverse event and that, for this reason, or due to the medication that may be instituted to reverse such event, it is considered that its continuation in the study is not pertinent.

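### An exclusion criterion without a time point allows patients with the most severe neuropathy to be withdrawn after randomisation, before their outcome is collected

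*Combined protocol and SAP*

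**What the plan says.** The following parts of the protocol bear on the point.

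- **Section 6.2** lists "Complication of peripheral polyneuropathy symptoms that require the use of specific medication" among the exclusion criteria and does not say when it is assessed. The lead-in to the list concerns entry: "Patients who meet one or more of the following criteria will not be eligible to take part in the study". A separate bullet covers "Pre-existing peripheral neuropathies not related to chemotherapy treatment".
- **Section 6.1** admits patients who have had no more than one chemotherapy session.
- **Section 7.1** says that subjects already in the study "may take any medication that their physician deems appropriate, excluding those specified in the exclusion criteria".
- **Section 7.3** reserves to the investigator the right to withdraw a subject. The first ground is "Subject abandonment: violation of inclusion or exclusion criteria or non-cooperation", and the reason is to be entered in the Data Notebook.
- **Section 6** defines the comparison: once treatment is finished, "the degree of cutaneous comfort will be compared between the patients who have developed peripheral neuropathy in both groups".
- **Sections 7.2 and 8.2** place the questionnaires at the end of chemotherapy, for patients who developed symptoms. Section 3 speaks instead of fortnightly questionnaires when there is discomfort.
- **Section 12** requires at least one use of the product and available satisfaction data for the MITT set, and adherence to the study instructions until the end for the per-protocol set.

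No section asks for outcomes after withdrawal, gives a missing-data method, or says how patients who start medication for neuropathy are analysed.

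**The concern.** With so little chemotherapy behind them at entry, few patients can already have neuropathy symptoms that need medication. Most who meet the criterion will do so during the study, as a consequence of the condition that defines the comparison group. If the exclusion list stays in force after randomisation, the patients most likely to be withdrawn are those doing worst.

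That is selection after allocation on something close to the outcome. Randomisation no longer protects the comparison, and a larger sample does not repair it. If one cream works better, fewer of its patients cross the threshold, and the survivors in the two arms look more alike than the arms really are. If withdrawal is applied unevenly, the arms can differ when the creams do not.

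**Working it through.** **Does the path to withdrawal exist?** Several neighbouring bullets in section 6.2 are tied to entry by a look-back period or by the word pre-existing; this one is not. Section 3 says that some doctors recommend antidepressants, such as duloxetine, for severe neuropathy. Antidepressants also appear in the first bullet of section 6.2, although its negation is garbled. Section 7.1 restricts excluded medications during the study, and section 7.3 lists an exclusion-criterion violation as a ground for withdrawal. A patient who starts such medication mid-chemotherapy can therefore be withdrawn before the questionnaire of sections 7.2 and 8.2.

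**The plan's own figure.** Section 6.3 gives a difference of 2, SD 3, significance level 0.05 and power 95%. Taking the test as two-sided:

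n per arm = 2 × (1.960 + 1.645)² × 3² / 2² = 58.5, so 59; the t-test version gives 59.5, so 60. The stated 60 is reproduced. Power at 60 per arm = Φ(2 / (3 × √(2/60)) − 1.96) = Φ(1.69) = 95.5%, or 95.2% by the t-test.

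**Common severity cut-off, true difference 2.** Assumptions: normal scores, SD 3, higher is better, worse-arm mean 0, better-arm mean 2, and every patient below one cut-off c removed. With a = (c − mean)/3 and λ = φ(a)/(1 − Φ(a)), the patients who remain have mean equal to the arm mean + 3λ, and SD 3 × √(1 + aλ − λ²).

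For 10% removed from the worse arm, c = −1.282 × 3 = −3.845.

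- Worse arm: mean = 3 × 0.1755/0.90 = 0.585.
- Better arm: a = (−3.845 − 2)/3 = −1.948, so 2.6% are removed; mean = 2 + 3 × 0.0598/0.974 = 2.184.
- Observed difference = 2.184 − 0.585 = 1.60.
- SE = √(2.53²/54.0 + 2.81²/58.5) = 0.503; power = Φ(1.60/0.503 − 1.96) = 89%.

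| Removed, worse arm | Removed, better arm | Left (worse / better) | SD (worse / better) | Observed difference | Power |
|---|---|---|---|---|---|
| 0% | 0% | 60 / 60 | 3 / 3 | 2.00 | 95% |
| 10% | 2.6% | 54.0 / 58.5 | 2.53 / 2.81 | 1.60 | 89% |
| 20% | 6.6% | 48.0 / 56.1 | 2.29 / 2.64 | 1.36 | 80% |
| 30% | 11.7% | 42.0 / 53.0 | 2.11 / 2.48 | 1.18 | 70% |

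For comparison, losing 10%, 20% or 30% of both arms at random leaves 54, 48 or 42 per arm and power of 93.4%, 90.4% or 86.3%. Selective removal loses fewer patients and costs more power, so the main harm is the selection and not the lost numbers.

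**Uneven removal, creams equal.** Removing the worst 20% of one arm raises its mean by 3 × 0.2800/0.80 = 1.05; removing the worst 10% of the other raises its mean by 0.585. The false difference is about 0.46. SE = √(2.29²/48 + 2.53²/54) = 0.477, and the two-sided rejection rate is about 16% instead of 5%. With 30% against 10%, the false difference is 0.91 and the rejection rate about 48%.

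**The case against.** The best defence is that section 6.2 governs entry only. Its lead-in speaks of eligibility, and section 7.2 applies the list as a condition of entering. The bullet also has a sensible entry-time meaning: its neighbour covers only neuropathy unrelated to chemotherapy, and one prior session is allowed, so it could exclude early chemotherapy-related symptoms. The violation in section 7.3 could be an entry error found later, and the disputed bullet names a complication and not a medication for section 7.1 to carry forward. All of this is arguable, but the protocol does not say it, and sections 7.1 and 7.3 prevent it from being assumed.

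A reader might also infer four stronger things that the documents do not support.

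- *That the criterion can be met only after randomisation.* One prior session makes entry-time cases possible.
- *That withdrawal is compulsory.* Section 7.3 reserves a right. This discretion is what makes uneven application possible.
- *That the reason for withdrawal is concealed.* The same bullet of section 7.3 sends it to the Data Notebook. What remains is that eligibility breaches and non-cooperation share one category.
- *That the bias always runs towards no difference.* Uneven removal can create a difference.

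Loss from the MITT set is also likely and not certain: if the fortnightly questionnaires of section 3 are the real schedule, a withdrawn patient may already have satisfaction data.

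The size is open to challenge as well. The documents give no removal share, and treating the need for medication as a perfect cut on the score is close to a worst case.

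**Conclusion.** The point holds as a gap in the plan: as written, it permits discretionary, severity-related withdrawal from the group that section 6 sets out to compare, with no rule for outcomes afterwards. Loss from the per-protocol set would follow, and loss from the MITT set is probable.

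The figures are illustrative. They rest on assumed removal shares, normal scores and a perfect severity cut. They use the 0 to 10 satisfaction scale of section 6.3, whereas section 8.1 makes the DLQI the main variable, so they describe the stated sample-size design and not the DLQI analysis. They also let all 60 per arm contribute. If 80% developed neuropathy, the upper figure for taxanes in section 3, the comparison would start from 48 per arm and 90.4% power before any withdrawal.

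This is a cheap improvement, and not a demonstration that the trial will be biased.

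**What to change.** Reconcile sections 6.2, 7.1 and 7.3 so that they say whether this criterion applies at entry only or also during the study. That choice is the sponsor's.

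Whichever applies, state the following in sections 7.3 and 12:

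- End-of-treatment outcomes are collected, subject to consent, from all randomised patients, including those who start medication for neuropathy or stop the cream.
- These patients stay in the MITT analysis, with the start of medication handled as a pre-specified intercurrent event.
- Medication starts and withdrawals are reported by arm, with reasons.

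The cost is wording in these sections and one added Data Notebook field. The downside is that outcomes in these patients will include the effect of the medication, which the report should say.
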